Aim II. Investigate the mechanisms through which mindfulness training impacts smoking cessation. Participants will complete questionnaires from baseline through 24 weeks after the start of treatment, in addition to intensive diary assessments for 6 contiguous weeks during treatment. We hypothesize that:

- 2a) Compared to UC, the mindfulness treatment arms (MBAT, iQuit Mindfully, and MBAT + iQuit Mindfully) will increase mindfulness; reduce negative affect (NA) and volatility of NA (i.e., greater affective stability); increase positive affect; reduce craving and withdrawal; and increase self-efficacy and social support, all of which will mediate effects of the mindfulness-based treatment arms vs. UC on abstinence.
- 2b) Compared to UC, MBAT, iQuit Mindfully, and MBAT + iQuit Mindfully will all attenuate links between NA/craving and smoking. That is, in addition to reducing NA and craving (2a), mindfulness training is hypothesized to weaken the relationships between NA/craving and smoking.

2c) Compared to MBAT, MBAT + iQuit Mindfully will produce stronger effects on the above mechanisms (2a, 2b). Mechanisms outlined in 2a will mediate effects of MBAT + iQuit Mindfully vs. MBAT on abstinence.

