Messages are personalized based on first names, personal reasons for quitting, and amount of money to be saved based on individual smoking habits and price paid per pack. Texts are also tailored based on responses to text questions (e.g., whether or not they have smoked or practiced mindfulness). Texts include messages timed around major holidays and personalized messages on participants' birthdays. Picture messages are included based on our initial qualitative work. Our previously developed program sent 2-3 messages per day during Week 1, 3-4/day during Week 2, 4-5/day during Week 3, 5-7/day during Week 4, 6-7/day during Week 5, 4/day during Week 6, and 3-4/day during Week 7 (See Appendix for example text messages and [name] et al. 2019²⁰ for details on the pilot study). Based on feedback from our previous message testing, message timing and frequency is more flexible and personalized for the current project. This study offers participants the option to be included in the frequency of their choice (e.g.: very low, low, medium, high, very high) as well as a 12-hour time slot of their choice (e.g.: 7am-7pm or 10am-10pm). Text messages will periodically ask participants about their preferred text message frequency and timing so that participants can change their message schedule as needed.

Financial Compensation and Retention Procedures. Participants receive financial compensation for the time and inconvenience associated with participation, as well as parking validation/MARTA vouchers to defray the cost of travel. Participants will be compensated up to \$30 for assessments during weeks 1, 3, and 5, for a total of \$90. (Specifically, for each of the week 1, 3 and 5 assessments, which take place online, participants will be compensated \$25 for doing the survey and a \$5 bonus if they do it within 24 hours). Participants will be compensated \$40 for the assessment completed at week 8 (this is an in-person visit). Participants will be compensated \$60 for the first post-treatment follow-up assessment at week 12 and \$70 for the second post-treatment follow-up assessment at week 24 (both follow-up visits are in-person visits). Participants will also be compensated \$5 per survey for the every other day surveys, for a total of \$120 for all 6 weeks. Maximum compensation per person for completing all aspects of the study is \$380.

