- Participants will complete *Program Evaluations* to provide for their feedback about and suggestions for improving the intervention (both MBAT and iQuit Mindfully text messages). Usual care participants will answer 1 program evaluation question: "On the scale below, please circle the number that best represents whether you would recommend this quit smoking program (or something similar) for others who are interested in quitting smoking." (rated on 1-10 scale).

The maximum time between telephone screening and enrollment will be 1 month. The maximum time between baseline assessment and start of treatment will be 1 month. However, we will employ a variety of strategies to ensure that these timeframes are as short as possible. For example, in order to reduce the time between telephone screening and baseline we will offer a variety of days and times for baseline assessment. We will also time our recruitment efforts around planned baseline assessments to maximize potential participants' interest (in order to prevent longer wait time to accrue a sufficient number of participants to start a group).

Electronic Diary Assessments. *Electronic Diary Assessments* (also referred to as short-surveys) will be administered in the evening on every other day from Week 2 to Week 8, thus capturing key processes surrounding quitting smoking. Diary assessments will assess smoking behavior ("How many cigarettes did you smoke today?") and each of the hypothesized mechanisms (mindfulness, emotions, craving and withdrawal, self-efficacy, and social support). Participants will also indicate their mindfulness practice that day (See Appendix). Participants will receive an email and/or text with the REDCap link to the electronic diary assessment survey. Both participant-initiated options allow respondents to complete assessments at a time that is convenient to them between that evening and the next morning (by 9am).

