9. STATISTICAL CONSIDERATIONS AND DATA ANALYSES

We will conduct both intent-to-treat (ITT) and per protocol analyses. ITT includes all participants that were randomized, regardless of compliance, withdrawal, and other events after randomization. A strength of ITT is that it is based on original randomization. However, effect estimation using ITT may be conservative and misleading with increasing attrition. Per protocol analysis considers only participants who fully complied and completed the study. Per protocol is less conservative and may reflect true treatment differences for those with full compliance. Including both approaches will provide a more complete understanding of treatment effects.

Analyses will be performed using SAS. Descriptive statistics for all measurements will be reported. Frequency distributions will be created to screen for any coding or entry errors. Frequency distributions summarize categorical data, and measures of central tendency and dispersion will summarize continuous data. All data will be examined for bivariate relationships with the outcomes and with each other. All analyses will control for demographics (age, gender, race/ethnicity, education level, partner status) and baseline nicotine dependence (cigarettes per day and time to first cigarette). The overall study level of significance will be α =.05.

Aim I. Test the efficacy of a mindfulness-based text messaging program for smoking cessation ("iQuit Mindfully"), both as a standalone intervention and in combination with virtual counseling.

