difference (MSSD; 48 average of the squared difference between successive observations at times i + 1 and i) to capture both within-person variability and temporal instability. Mediation will be examined with multilevel mediation analyses for binary outcomes in the developed GzLMM. Bootstrapping with 5000 replications will be used to estimate standard errors and p-values for indirect effects. In addition to mediators of associations between treatment and abstinence outcomes, we will test more fine-grained day-to-day associations using electronic daily diaries.

We will test moderated mediation using a model proposed by Preacher, Rucker, and Hayes⁴⁹ that fits the hypothesized model (Figure 3), as the independent variable (mindfulness training) also functions as a moderator. Kline⁵⁰ termed this "second-stage moderation," as the second path of the indirect effect of the predictor on the dependent variable depends on the moderator. Conditional mediation and moderation effects will be tested using bootstrapping methods.⁴⁹ GzLMM provides an ideal method for assessing the proximal relation between negative affect/craving at a given assessment and smoking at the next assessment (using both questionnaire and daily diary data). For example, using daily diary assessments, we will examine whether the association between negative affect on a given day and next-day smoking is weaker among MBAT vs. UC participants.

Missing Data. Although there is no complete, comprehensive method for handling missing data for generalized linear mixed models, there are several different approaches that we can draw upon to address this issue.⁴⁴ We will use multiple imputation of missing data whereby missing observations for individuals are estimated based on baseline responses and other study covariates, and perform additional sensitivity analyses regarding various missing data assumptions for smoking outcomes.⁵¹

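### Raw MSSD for negative affect is planned without a mean-affect term or joint entry with affect level, so if diary scores sit near the scale floor, a fall in level alone can appear as reduced volatility

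*Combined protocol and SAP*

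**What the plan says.** Hypothesis 2a (Section 1, Aim II) states that the mindfulness arms will "reduce negative affect (NA) and volatility of NA (i.e., greater affective stability"), alongside other changes, "all of which will mediate effects of the mindfulness-based treatment arms vs. UC on abstinence". Level and volatility of NA are therefore two entries in one list of hypothesised mediators.

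Section 9, Aim II, defines volatility as MSSD, the "average of the squared difference between successive observations at times i + 1 and i", and gives its purpose as "to capture both within-person variability and temporal instability".

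On covariates, Section 9 says "All analyses will control for demographics (age, gender, race/ethnicity, education level, partner status) and baseline nicotine dependence". The Aim I model adds treatment condition, time and their interaction. On mediation it says "Mediation will be examined with multilevel mediation analyses for binary outcomes in the developed GzLMM", with bootstrapped indirect effects. It does not say whether mediators enter singly or together, and it names no term for the person's average affect. Mediation is to be tested whether or not the intervention effect is significant.

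The diaries are "administered in the evening on every other day from Week 2 to Week 8" (Section 6.2). The items are referred to an appendix that is not among the documents, so neither the response range nor typical scores can be read.

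**The concern.** On a scale with a lower bound, a person whose scores cluster at the bottom has little room to move, so successive differences are small. If treatment lowers average NA, as 2a predicts, more people move into that region and MSSD can fall although nothing about their underlying stability has changed. A model with raw MSSD and no information on level cannot then separate feeling less bad from being more stable.

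What is at stake is how a mechanism finding is interpreted. One change in level could be reported as two mechanisms. The same applies to 2c, which repeats the 2a mechanisms for MBAT + iQuit Mindfully vs MBAT. The primary abstinence comparisons are not affected.

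**Working it through.** The plan gives no figure for volatility, so there is none to reproduce.

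**Inputs from the documents**
- Arms: 145 per treatment group and 50 in usual care. With the stated 20% attrition, 145 x 0.8 = 116 and 50 x 0.8 = 40.
- Diaries: $5 "per survey for the every other day surveys, for a total of" $120, so 120 / 5 = 24 entries. Six weeks on alternate days would give 42 / 2 = 21.
- Two-sided alpha of 0.05.
- Exclusion of PHQ-2 scores of 3 or above, which makes low NA plausible but fixes no diary mean.

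**Assumptions (none is in the documents)**
- A 1-5 scale.
- Between-person SD 0.6, within-person SD 0.6, lag-1 autocorrelation 0.3.
- Identical latent variability in both arms; treatment lowers only the mean.

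**Step 1: without a bound there is no artefact.** Adding a constant c to every score leaves the measure unchanged, because (x[i+1] + c) - (x[i] + c) = x[i+1] - x[i]. For this process the expected MSSD is 2 x 0.6² x (1 - 0.3) = 0.504. The simulation gave 0.504 before and 0.503 after a fall in the mean.

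**Step 2: with a bound, it depends on where scores sit.** Total SD is √(0.6² + 0.6²) = 0.85, and a fall of 0.3 SD is 0.255 points. Each diary score is the average of five items; there were 1500 trials per cell. MSSD was regressed on arm, without and with the person's mean and its square (two-sided, robust standard errors).

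| Latent mean | MSSD before, after | Fall | False effect, 40 vs 116 | False effect, 116 vs 116 | With mean and mean² (40 vs 116; 116 vs 116) |
|---|---|---|---|---|---|
| 3.0 | 0.602, 0.597 | 1% | 4.7% | 5.5% | 5.4%; 4.7% |
| 2.0 | 0.505, 0.451 | 11% | 26.9% | 50.5% | 4.5%; 5.1% |
| 1.75 | 0.452, 0.386 | 15% | 37.0% | 61.1% | 4.3%; 5.5% |
| 1.5 | 0.387, 0.316 | 18% | 40.9% | 68.2% | 5.9%; 4.3% |

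A fall of 0.5 SD (0.425 points) gave 57-85% at 40 vs 116 for means of 1.5 to 2.0, and 5.7-9.5% at mid-scale across both sample sizes. Across all scenarios the adjusted rate was 3.5-6.1%.

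**Step 3: smaller shifts.** Taking the fall as 0.3-0.5 of the between-person SD alone gives 0.3 x 0.6 = 0.18 to 0.5 x 0.6 = 0.30 points. At 40 vs 116, the share of trials significant in the direction of reduced volatility was 24-51% at mean 1.5, 11-34% at 2.0, 5-11% at 2.5 and about 3% at 3.0. Chance in one direction is 0.05 / 2 = 2.5%. With the mean and its square the rate was 4-7%.

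**Step 4: does it reach the mediation claim?** Abstinence was made to depend on mean NA only (log-odds 0.5-0.8 per SD), with the falls of Step 3. At 40 vs 116, a false indirect effect through volatility appeared in 9-43% of trials at mean 1.5, 4-23% at 2.0 and 1% or less at mid-scale. With mean NA in both equations it was about 0%. This used one abstinence outcome and a Monte Carlo interval, not the planned repeated-measures bootstrap, so it shows direction and rough size only.

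**The case against.** Four points can fairly be made for the plan.

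1. *The condition cannot be checked.* Response range, item count, means, SDs and autocorrelation of the diary NA items are all unknown here. This stands. The rates above are conditional and are not predictions for this trial.

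2. *Silence is not a rule.* Section 9 writes out no mediator equation, and NA level is itself a listed mediator, so joint entry may be intended. A reader might infer that the plan excludes adjustment for level; the text does not support that. It leaves the choice open, and the choice decides the interpretation when scores are low.

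3. *2a does not claim independence.* It lists volatility beside level without saying that one acts apart from the other. This stands too, and it limits the remedy to how a positive volatility result may be described.

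4. *Adjustment has its own cost.* Mean NA over the same diaries is measured after randomisation and is a hypothesised mediator. Conditioning on it changes the question and is conservative if greater stability is what lowers the mean; the simulations did not test that case. It would therefore be too strong to accept volatility only from the adjusted model and discard the raw result.

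**Conclusion.** The concern holds in conditional form. NA level and NA volatility are both hypothesised mediators, volatility is raw MSSD, and neither a mean-affect term nor joint entry is specified. If the diary scale is bounded and scores sit near the floor, a fall in average NA alone produces apparent stability. Under the assumptions above (40 vs 116, fall of 0.18-0.30 points) that is a false result in about 24-51% of trials at mean 1.5, 11-34% at 2.0 and 5-11% at 2.5.

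A reader might infer that every fall in average NA will register as lower volatility on a scale with a floor. It will not: at mid-scale on the same 1-5 scale, falls of this size change nothing beyond chance, and without bounds MSSD ignores level altogether. Nor do the documents show that this trial's scores will be low; the PHQ-2 exclusion makes it plausible and no more. The point concerns one Aim II mechanism. It is worth acting on because the remedy uses data already being collected.

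**What to change.** In Section 9, Aim II, add wording to this effect:

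*Models with NA volatility as outcome or mediator will be reported (a) unadjusted and (b) with the person's mean NA from the same diaries, linear and quadratic; alternatively, NA level and NA volatility will enter as joint mediators. Volatility will be described as a mechanism distinct from NA level only if its effect persists after this adjustment. Otherwise it will be reported as not separable from level.*

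The cost is a few lines in the analysis plan, one derived covariate and its square, and a second column of results; no new data are needed. The drawback is that the adjusted estimate is conservative if volatility drives the mean, which is why both results are shown. If diary scores prove to be mid-scale, the two should differ little.

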The relationship between treatment condition and each dichotomous study outcome (smoking cessation, lapse recovery) will be assessed with a generalized linear mixed model (GzLMM) with a Binomial distribution and logit link function. This is an appropriate statistical model with repeated measures data collected over time. ⁴⁴ A 2-level multilevel GzLMM will be specified, with time nested within subject. This approach will properly account for the multilevel data structure. Fixed effects considered in each model will include demographics, baseline nicotine dependence, treatment condition and time as main effects, and a treatment condition by time interaction. Testing of covariance structure will be conducted, and information criteria will be used to assess model fit and selection. Linear contrasts will be built into the analysis to estimate specific comparative effects of all treatment conditions. To test treatment effects on primary smoking cessation outcomes, repeated measures outcomes will be biochemically-confirmed 7-day point prevalence abstinence at weeks 8, 12, and 24. To test treatment effects on lapse recovery, this analysis will also be conducted among participants classified as smoking at the last treatment session. ¹² In addition, gender and race/ethnicity will be assessed as potential moderators of treatment effects.

The moderating effect of poverty status will be examined with the addition of a poverty status by treatment condition interaction into the models described in 1a). This will be tested using both dichotomous (i.e., below vs. at or above federal poverty threshold) and continuous poverty status variables (i.e., depth of poverty as indicated by income-to-poverty ratio and income deficit/surplus) according to U.S. Census guidelines.^{45,46}

Aim II. Investigate the mechanisms through which mindfulness training impacts smoking cessation.

Hypotheses regarding mechanisms will be tested with both traditional questionnaire data (collected from baseline through 24 weeks after the start of treatment) and electronic diary data (collected for 6 continuous weeks during treatment), separately. Mediation testing will be conducted regardless of statistical significance of intervention effects because of statistical, conceptual, and practical reasons for testing mediation in such cases.⁴⁷ Volatility will be calculated using the mean square successive

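### The diary test of hypothesis 2b has no term for smoking at the current diary, so smoking carry-over can create or mask an apparent weakening of the affect/craving-to-smoking link

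*Combined protocol and SAP*

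**What the plan says.** Section 1 states hypothesis 2b: "mindfulness training is hypothesized to weaken the relationships between NA/craving and smoking". Section 9, Aim II, tests it with a generalized linear mixed model, presented as suited to "assessing the proximal relation between negative affect/craving at a given assessment and smoking at the next assessment". As its diary example, it asks whether "the association between negative affect on a given day and next-day smoking is weaker among MBAT vs. UC participants".

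The adjustments named are these:
- For every analysis: "All analyses will control for demographics (age, gender, race/ethnicity, education level, partner status) and baseline nicotine dependence".
- In the Aim I model, the list of terms: "considered in each model will include demographics, baseline nicotine dependence, treatment condition and time as main effects, and a treatment condition by time interaction".
- For clustering: "A 2-level multilevel GzLMM will be specified, with time nested within subject".

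Section 6.2 (Electronic Diary Assessments) says: "Diary assessments will assess smoking behavior". The item asks for the number of cigarettes that day. The same form carries the hypothesized mechanisms, including emotions, craving and withdrawal. Smoking at the current diary is therefore collected, but no section names it as a covariate in the 2b model. The plan is silent on it rather than deciding against it.

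**The concern.** Smoking today predicts smoking at the next diary. It may also shift the affect or craving reported this evening. It can thus be a common cause of both ends of the tested link. Baseline covariates and a person-level random effect absorb stable differences between people, not carry-over from one diary to the next.

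Section 1 (hypothesis 1a) expects treatment to improve cessation and lapse recovery, so smoking transitions are expected to differ by arm. The treatment-by-affect term may then reflect altered carry-over rather than altered reactivity to affect. A mechanism claim under Aim II could in that case be a by-product of the Aim I effect, or a real weakening could be hidden.

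**Working it through.** **Inputs from the documents.**
- 145 MBAT and 50 usual care (UC), each less 20% attrition: 145 × 0.8 = 116 and 50 × 0.8 = 40.
- $120 at $5 per survey: 120 / 5 = 24 diaries, or 23 lagged pairs. Diaries come every other day, so the next diary is two days later, not the next day.
- Two-sided α = .05, so 2.5% in the direction of attenuation.
- Effect sizes d = 0.33 and 0.35. The plan gives no figure for this diary test, so there is none to reproduce.

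**Assumed, because the documents give no values.** The transition probabilities of smoking, and the effect g of a smoking day on evening affect, in residual SD.

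**Why the sign varies.** Let S be smoking (0/1) and A = g·S + noise. Let p11 be the chance of smoking at the next diary after a smoking diary, and p01 the chance after an abstinent one. If A has no effect on later smoking, then, ignoring differences between people, cov(A at t, S at t+1) = g × (p11 − p01) × var(S).
- Lowering p11 alone shrinks the spurious link.
- Lowering p01 alone widens it.
- Lowering both in step changes the gap p11 − p01 much less.
- Reversing the sign of g reverses everything.

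**Simulation.** True effect of affect on later smoking is zero; 200 trials per row; random-intercept logistic model. The planned model has affect, arm, time, arm × time and arm × affect. Entries are the arm × affect coefficient and the rate of significant attenuation.

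| Scenario (UC vs MBAT) | Planned model | + current smoking | + current smoking and arm × current smoking |
|---|---|---|---|
| Smoking does not change affect | 0.000; 2.0% | 0.001; 1.5% | 0.003; 2.0% |
| p11 0.85 vs 0.75, g = 0.5 | −0.039; 7.5% | −0.050; 8.5% | 0.001; 2.0% |
| p11 0.85 vs 0.65, g = 0.5 | −0.076; 12% | −0.084; 15% | 0.003; 2.0% |
| Same, with between-person SD 1 | −0.075; 9% | −0.087; 10% | 0.017; 1.5% |
| p11 0.85 vs 0.65, g = 1.0 | −0.146; 46.5% | −0.152; 54% | 0.003; 2.0% |
| p11 0.92 vs 0.80, g = 0.8 | −0.055; 5.5% | −0.110; 18.5% | 0.009; 1.0% |
| Both transitions −0.7 on logit, g = 0.5 | −0.008; 3.5% | 0.002; 2.0% | 0.003; 2.0% |
| Fewer relapses only, g = 0.5 | +0.037; 1.0% | +0.076; 0.5% | 0.003; 3.0% |
| p11 0.85 vs 0.65, g = −0.5 | +0.076; 0% | +0.085; 0% | 0.003; 2.0% |

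In the last row the planned model was significant in the opposite direction in 15% of trials. Whenever smoking raised affect, the planned model's UC slope was about 0.28 to 0.54, although the true slope was zero. The Monte Carlo standard error is at most √(0.465 × 0.535 / 200) = 3.5 points; at 7.5% it is 1.9 points.

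**Which row is near the plan's effect size.** Converting d to log-odds by π/√3 = 1.814 gives 0.33 × 1.814 = 0.60 and 0.35 × 1.814 = 0.63. The gap 0.85 vs 0.75 is logit(0.85) − logit(0.75) = 1.735 − 1.099 = 0.64. The scales differ (abstinence at follow-up against diary transitions), so this is only a guide. Two further runs with log-odds persistence of 2.5 vs 1.9 gave 5% and 8%. At 2.5 vs 1.5, one run gave 15%.

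**The case against.** **Adjustment may remove the effect of interest.** This is the strongest objection. Cigarettes and affect come from one evening form, so their order within the day is unknown. If craving drives smoking the same day, current smoking is a mediator. In simulations with a true same-day attenuation (slope 1.0 in UC, 0.2 in MBAT, equal persistence, affect autocorrelation 0, 0.3 and 0.5), the unadjusted model detected it in 42%, 76% and 90% of trials. The adjusted model detected it in 0%, 2.5% and 11.5%. A separate run fell from 84% to 28%. This stands: the adjusted model cannot be the sole test.

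**The plan is silent, not wrong.** The diary test is introduced as an example, the detailed list of fixed effects belongs to Aim I, and the figure for the hypothesized model is not shown. That is fair. It makes this a gap to close rather than a stated error.

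**The model might correct itself.** Section 9 (Aim I) allows testing of covariance structures. In a check with a first-order autoregressive structure, the spurious slopes disappeared but the difference between arms did not. This objection fails.

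**Shorter lapses need not look like a weaker link.** A reader might infer that any success in lapse recovery would show up as attenuation. The documents do not support that. Hypothesis 1a predicts more cessation as well as more lapse recovery. Section 9 examines lapse recovery among those smoking at the last session, not by spell length in the diaries. With an equal logit benefit on both transitions, lapses shorten (0.85 to 0.74) and false attenuation is 3.5%.

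**Conclusion.** The concern holds as a should-fix point for one mechanism hypothesis. The planned diary contrast cannot separate reactivity to affect or craving from smoking carry-over, and the resulting bias can create or mask attenuation. Two conditions are needed: a day's smoking must move evening affect or craving, and treatment must change continuation and relapse unequally on the logit scale. The documents establish neither, nor the sign of the first.

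Near the plan's effect size the inflation is modest, about 5 to 8% against 2.5%. A reader might take the high rates as typical: 46.5% above, or the 10 to 90% seen in runs with persistence gaps of 1.0 to 2.0 log-odds and no attrition. They are not typical, because they rest on large assumed gaps placed wholly on persistence, or on a strong effect of smoking on affect. Even a larger gap does not guarantee a high rate: 0.92 vs 0.80 gave 5.5%.

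The simulations treat smoking as yes/no, omit the demographic and baseline covariates, and cover MBAT against UC only. The primary abstinence analyses under Aim I are untouched.

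**What to change.** In section 9, Aim II, prespecify a second diary model for 2b. It adds smoking at the current diary and its interaction with treatment condition to the planned terms. State how current smoking is coded. The interaction is needed: the main effect alone left 15% false attenuation where the planned model had 12%.

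Report the two models side by side, with a rule for interpretation:
- Claim a weakened link from affect/craving to later smoking, distinct from changed carry-over, only if the treatment-by-affect/craving term also holds in the second model.
- If only the planned model shows attenuation, state that carry-over and a same-day pathway cannot be told apart.

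Keep the planned test. The second model has low power for a same-day pathway, and a lagged outcome with a random intercept brings a small initial-condition bias, minor with about 20 diaries per person. The cost is a few lines of SAP text and one further model, with no new data collection.

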Power and Sample Size Determination. Sample size was estimated based on the number of participants needed to detect meaningful treatment effects of the iQuit Mindfully and MBAT interventions. We obtained effect sizes (converted to Cohen's *d* for comparability across measures) from relevant meta-analyses and used the Optimal Design program to estimate sample size for GzLMM models. Samoking abstinence in MBIs vs. UC was quantified as *d*=0.35 in a meta-analysis, and a Cochrane review of primarily text messaging-based interventions for smoking cessation concluded an effect size of *d*=0.33. Assuming 80% power, level of significance of .05, two-tailed statistical tests, error variance of 1.0, coefficient variance of 2.0, and oversampling to account for 20% attrition, this results in 145 participants in each treatment group. An unequal allocation ratio was used to allocate fewer participants to usual care (*n*=50), 55,56 for an overall sample size of 485 participants (145 per treatment group and 50 in usual care). We expect this sample size to adequately allow for mediational testing (Aim 2) at the 80% power level. Fritz and MacKinnon for offer a guide regarding sample size required to detect mediated effects and report that 79.9% of studies in their literature review applied mediational testing with less than 400 subjects, suggesting our study plan with 485 subjects will be ample for achieving all study aims.

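### The 80% power for 145 per group comes from a continuous-scale calculation; for the planned yes/no abstinence analysis it holds only under conditions the plan does not state

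*Combined protocol and SAP*

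**What the plan says.** The sample-size paragraph of Section 9 takes two effect sizes from the literature, both expressed as Cohen's d. For mindfulness interventions, abstinence "in MBIs vs. UC was quantified as *d*=0.35 in a meta-analysis"; for text messaging, a review "concluded an effect size of *d*=0.33". The calculation was run in the Optimal Design program. Its conditions are "Assuming 80% power, level of significance of .05, two-tailed statistical tests", with "error variance of 1.0, coefficient variance of 2.0". The result is given as "oversampling to account for 20% attrition, this results in 145 participants in each treatment group". Usual care is then set at 50, for a total of 485.

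The Aim I analysis, also in Section 9, is a "generalized linear mixed model (GzLMM) with a Binomial distribution and logit link function". It is fitted to biochemically confirmed abstinence at weeks 8, 12 and 24, with treatment, time and their interaction, and with linear contrasts between conditions.

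The plan does not state the number or duration of measures entered in the program, the scale on which d is standardised, the sample size before inflation, which d or which contrast produced 145, or any abstinence rate for planning. It also does not say whether the contrasts are taken at each visit or averaged over visits.

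**The concern.** The power of a comparison of proportions depends on the proportions. A d with an error variance of 1.0 describes a continuous outcome, so the 80% does not carry over to a logit model of abstinence without a comparator rate and a within-person correlation for yes/no data.

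The printed number also invites a second look: 145 is what a simple two-group formula gives for d=0.33 before any allowance for attrition.

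The contrast at stake is MBAT + iQuit Mindfully versus MBAT, the first comparison in hypothesis 1a (Section 1). Both arms have 145, so the small usual-care arm is not involved. If power is well under 80%, a null result could be read as good evidence that texting adds nothing to MBAT when the trial could not show that.

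**Working it through.** **Inputs from Section 9.** Two-sided alpha 0.05 (z = 1.960); power 80% (z = 0.842); d = 0.33 (text messaging) or 0.35 (mindfulness); error variance 1.0 and coefficient variance 2.0; attrition 20%, so 145 × 0.8 = 116 per arm. For the contrast examined, which adds texting to MBAT, 0.33 is the closer match; both are shown.

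**Step 1: the plan's figure, one measure.** n = 2(1.960 + 0.842)²/d².
- d = 0.33: 144.1, so 145 with no attrition; 144.1/0.8 = 180.2 with it.
- d = 0.35: 128.1; 160.2 with attrition.

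**Step 2: the plan's figure, mean of three visits.** Assume that the variances are a random intercept of 2.0 and a residual of 1.0, and that d is standardised by the total SD. The variance factor is (2 + 1/3)/3 = 0.778.
- d = 0.33: 144.1 × 0.778 = 112.1; 112.1/0.8 = 140.1, or 142 when rounded up at each stage. This is within 3% of 145.
- If d is standardised by the coefficient SD instead, the factor is (2 + 1/3)/2 = 1.167, giving 169, or 212 with attrition. This does not match.

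So 145 agrees exactly with a one-measure calculation without attrition, and approximately with a three-visit calculation that includes it. The document does not settle which was used.

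**Step 3: power at 116 per arm on the d scale.** Power = Φ(d√(n/2) − 1.960), with n divided by 0.778 for three visits.
- One visit: 0.33 × √58 = 2.513, giving 71%; 0.35 × √58 = 2.666, giving 76%.
- Three-visit mean: 81% and 86%.

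**Step 4: power at 116 per arm on the abstinence scale.** Assume ln OR = dπ/√3, so OR = 1.82 or 1.89. With comparator rate p1 and the resulting p2, SE² = f1/(116 p1q1) + f2/(116 p2q2). For one visit f = 1; for a three-visit average f = (1 + 2ρ)/3, where ρ is the correlation between a person's yes/no outcomes. Power = Φ(ln OR/SE − 1.960).

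Example, d = 0.33 and p1 = 20%: p2 = 31.3%; SE² = 1/(116 × 0.160) + 1/(116 × 0.215) = 0.0940; SE = 0.307; 0.599/0.307 = 1.95; power 50%. With three visits and ρ = 0.67, f = 0.778, SE = 0.270, power 60%.

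Three versions of ρ were used, all assumptions:
- 0.67, the ratio 2/(2 + 1) applied directly to yes/no data;
- 0.38-0.47, from the same variances in a latent threshold model;
- 0.17-0.27, from 2.0 as the random-intercept variance of the logit model, with the OR kept as the marginal effect.

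Power in %, d = 0.33 / d = 0.35:

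| Comparator abstinence | One visit | Three visits, ρ = 0.67 | Three visits, latent | Three visits, logit |
|---|---|---|---|---|
| 10% | 33 / 36 | 40 / 45 | 50 / 55 | 61 / 66 |
| 15% | 42 / 47 | 52 / 57 | 62 / 67 | 72 / 78 |
| 20% | 50 / 55 | 60 / 65 | 70 / 75 | 79 / 84 |
| 30% | 58 / 63 | 69 / 74 | 78 / 82 | 86 / 90 |

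Over all comparator rates, one-visit power peaks at 62% / 67%.

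**The case against.** The best defence is Step 2. The plan used a repeated-measures program, listed two variance components, and names three outcome visits. A three-visit mean uses all of that, comes within 3% of 145 with attrition included, and gives 81% at 116 per arm. The one-visit formula ignores the variances, so its exact match to 145 may be coincidence. This stands. A reader might infer from Step 1 that attrition was simply forgotten; the documents do not support that, and rewriting the attrition sentence on that basis could replace a true statement with a false one. Nor do they confirm the favourable reading, since the scale of d and the number of measures are unstated.

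A reader might also infer that power is below 80% at every abstinence rate, because with ρ = 0.67 three-visit power peaks at 72% (d=0.33) or 77% (d=0.35). That puts a continuous-scale correlation onto yes/no data. With the latent or logit versions, power reaches 80% or more at comparator rates of roughly 20-40%, depending on d and ρ.

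Two further points have weight. The odds-ratio conversion is an assumption; if d is read as Cohen's h, one-visit power at d=0.33 is 69-71%, little different from the d scale, though still under 80%. And 116 is cautious: it drops 20% of people from all three visits, whereas the plan has intent-to-treat analysis, a mixed model and multiple imputation. However, 116 follows from the plan's own attrition figure. Even with all 145 analysed, one-visit power on the odds-ratio scale peaks at 71% or 76%.

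**Conclusion.** The concern holds as a gap between the power statement and the analysis it is meant to support, not as a proven arithmetic error. The unqualified 80% is a continuous-scale figure, and its transfer to abstinence is neither shown nor possible to check from the document.

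Two results hold under every version tried. At 116 per arm, power at a single primary visit is below 80% on the d, odds-ratio and Cohen's h scales. With the odds-ratio conversion, three-visit power is also below 80% whenever comparator abstinence is 15% or less: 52-78% at 15% and 40-66% at 10%. At 20% the range is 60-84% and at 30% it is 69-90%, so the claim may be met there, depending on the correlation and on which d applies.

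These figures rest on 20% loss at all three visits, the d-to-odds-ratio conversion, a contrast averaged equally over visits, and the three assumed correlations. Severity: should be fixed. N, the analysis model and type I error are unaffected.

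**What to change.** Keep N=485. In the sample-size paragraph of Section 9:

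- Replace the single 80% with power for each contrast named in hypothesis 1a, at post-attrition numbers (116 versus 116 between treatment groups; 116 versus 50 × 0.8 = 40 against usual care), on the odds-ratio scale, over a stated range of comparator abstinence and within-person correlation for yes/no outcomes.
- State whether each contrast is per visit or averaged over weeks 8, 12 and 24, and match the power to that choice.
- Report the Optimal Design settings (number and duration of measures, scale of d, contrast powered) and the sample size before inflation. The 20% attrition statement can then be confirmed, or corrected if it proves wrong.

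The cost is SAP wording and a short simulation from the planned logit mixed model, with no added participants. The downside is that the stated power will probably look less favourable.
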